3.1 Interim analysis and sample size re-estimation

The trial has a traffic light system incorporated at 15 months to assess progression from the internal pilot phase to full trial. Criteria for the traffic light system are based upon

Statistical Analysis Plan

recruitment rates (both number of sites and participants) and adherence to the intervention and control. If the red criteria are met, the trial would stop at this point. Full details can be found in section 16.3 of the protocol.

The trial will use a group sequential design with O'Brien-Fleming boundaries to inform early stopping of the trial in the case of strong evidence of harm or benefit, while preserving the overall 5% type I error rate for the trial. Two interim analyses to test for harm or benefit will be conducted after 70 and 100 patients have been recruited into the trial with primary outcome data. The stopping rules will be used as a guideline, alongside the other safety data available to the DMC, and used as part of their overall assessment of the trial.

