For each participant, all plasma sodium concentrations measurements which are ≥5mmol/l and which were taken between transplant operation start and 72 hours post-transplant will be compared. The rate of change will be calculated, for tests taken at least six hours apart, by taking the difference between the measurements and dividing by the number of hours between the measurements. The maximum decrease of these will be selected for each participant. The mean maximum rate, with standard deviation, will be presented for each trial arm and overall. A Normal linear regression model will be used to assess whether mean maximum rate is different between the two treatment arms, adjusting for donor type (living vs deceased donor), participant weight pre transplant (<20kg vs ≥20kg pre-transplant) and transplant centre as a random effect. Residual plots from the normal linear regression will be examined. If there is any evidence of skew or non-constant variance, normal linear regression of log-transformed maximum rate will be used to assess whether mean log- maximum rate are different between the two treatment arms, adjusting for donor type (living vs deceased donor), participant weight pre transplant (<20kg vs ≥20kg pretransplant) and transplant centre as a random effect.

Serious adverse events

Serious adverse events will be tabulated by classification (Acute severe hyponatraemia – symptomatic and non-symptomatic (separately), severe hyperkalaemia, seizures and other) and treatment arm. The number of participants who experienced at least one SAE will also be presented. Following the implementation of protocol v2.0, SAEs relating to electrolytes were no longer required to be reported by sites. Therefore, both acute severe hyponatraemia and severe hyperkalaemia will also be identified through all participants' plasma and blood gas results, including those SAEs which occurred prior to the protocol change. Acute severe hyponatraemia is defined as: a fall in plasma or blood gas sodium concentration of ≥10mmol/L from the pre transplant level or a rate of fall of plasma or blood gas sodium concentration exceeding 1mmol/L/hour averaged over 6 hours. A plasma or blood gas potassium concentration >6.5mmol/L will be used to identify acute severe hyperkalaemia. No statistical testing will be conducted.

Graft and patient survival at 90 days

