3.8 Procedures for handling Missing Data

Any missing primary and secondary outcome data will be summarised. For the primary outcome and other blood test results, the result will be considered missing if there are no results for that measurement within the 72-hour period post transplant. It is anticipated that missing data for the primary outcome will be rare, as the plasma sodium measurement is also used to determine one of the key SAEs within the trial, which mandates immediate reporting. Missing data due to death or withdrawal are also anticipated to be very rare: data from the UKTR showed that the 1-year patient survival rate for those transplanted between 2015-2018 was 99% (95% confidence interval 96-100) for paediatric kidney transplants from living and DBD donors (5). Primary and secondary outcome measures will not be imputed and these will be treated as missing data and excluded from the relevant analyses. If outcome data is missing for more than 25% of participants, outcomes will not be reported.

To explore if missing values have an undue impact on the primary outcome result, a sensitivity analysis using multiple imputation will be performed if the primary outcome is missing in more than 5% of the participants included in the modified intention to treat analysis. Variables will be included in the imputation model if they have a completeness of ≥65% and these variables are:

- Donor: type, age, ethnicity, BMI
- Trial participant/Recipient: age, sex, ethnicity, cause of end stage kidney disease, native urine output, dialysis type, weight and height at transplant, systolic blood pressure, blood group, calculated reaction frequency, graft number
- Transplant: blood group match, transplanting centre, cold ischaemic time, HLA mismatch between donor and recipient, graft placement.

Forty imputations will be used and the average across the imputations will be calculated. The model specified in section 3.3 will be utilised.

If the proportion of participants with a missing primary outcome is less than or equal to 5% then this sensitivity analysis will not be performed.

Statistical Analysis Plan

All the risk adjustment factors will always be known, as weight and site are required for randomisation and donor type is mandatory data required by the UKTR.

4. Data Analysis Tables

Data analysis will be based on the following tables.

- 4.1 Screening, Recruitment and Follow-up tables
 - 4.1.1 Recruitment by Centre

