4.5 Other Outcome summary tables

| Randomised | l Treatment | |
|----------------------------|--|-------------------------|
| (n=) | 148 (n=) | Total (n=) |
| sodium concentration | n | |
| | | |
| | | |
| | | |
| | | |
| | | |
| | | |
| | | |
| | | |
| | | |
| n in first 72h (mmol/L) | l l | |
| | | |
| | | |
| | | |
| ation in first 72h (mmol/L | /hours) | |
| | | |
| | | |
| | | |
| blood gas | | |
| 5100a gao | | |
| | I | |
| | | |
| | Standard care (n=) sodium concentration n in first 72h (mmol/L) | n in first 72h (mmol/L) |

Adjusted for site, participant weight pre transplant and donor type.
 p-value from the likelihood ratio test when including and excluding the treatment term from the model.
 N is the number of primary outcome events

Statistical Analysis Plan

| | Randomised | Treatment | |
|--|------------------------|-----------------------------|----------------|
| | Standard care (n=) | Plasma-Lyte 148 (n=) | Total (n=) |
| Serious adverse events | | | |
| Total number of events | | | |
| Acute severe hyponatraemia (symptomatic) n(%)1 | | | |
| Acute severe hyponatraemia (non-symptomatic) n(%)1 | | | |
| Severe hyperkalaemia n (%)¹ | | | |
| Seizures n(%) | | | |
| Other n(%) | | | |
| Number of participants experiencing at least one SAE (% of total number of participants) | | | |
| Serious adverse events (identified from plasma and blood gas results) ² | | | |
| Total number of events | | | |
| Acute severe hyponatraemia n(%) | | | |
| Excessive rate of reduction in sodium concentration n(%) | | | |
| Excessive magnitude of reduction in sodium concentration n(%) | | | |
| Severe hyperkalaemia n(%) | | | |
| Number of participants experiencing at least one SAE (% of total number of participants) | | | |
| · | | | |
| Survival at 90 days | | | |
| Graft % (95% CI) | | | |
| Patient % (95% CI) | | | |

² Includes events reported prior to v2.0 of the protocol.

Statistical Analysis Plan

| Table XX Other outcome measure – volume of | intravenous fluid re | ceived | |
|--|-------------------------|-----------------------------|----------------|
| | Randomised | l Treatment | |
| | Standard care (n=) | Plasma-Lyte 148 (n=) | Total (n=) |
| Summary of IV fluid volume received | | | |
| N (%) participants who received at least one IV fluid | | | |
| Median (IQR) intravenous fluid volume (ml/kg body weight) per participant per occasion | | | |

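### The SAE table's total and any-SAE rows mix two reporting periods, and no row counts participants with any SAE over the whole trial

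*SAP*

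**What the plan says.** SAP section 3.5, under serious adverse events, sets the layout: "Serious adverse events will be tabulated by classification (Acute severe hyponatraemia – symptomatic and non-symptomatic (separately), severe hyperkalaemia, seizures and other) and treatment arm". It also promises the number of participants with one or more SAEs. It then discloses a change during the trial: "Following the implementation of protocol v2.0, SAEs relating to electrolytes were no longer required to be reported by sites". The remedy follows directly: "both acute severe hyponatraemia and severe hyperkalaemia will also be identified through all participants' plasma and blood gas results", including events from before the change. The laboratory definition of severe hyponatraemia is purely biochemical. One limb is "a fall in plasma or blood gas sodium concentration of ≥10mmol/L from the pre transplant level", and the other is a rate of fall. SAEs are descriptive and are not tested.

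The SAE table in section 4.5 has two blocks.

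- **Site-reported block.** Its rows are an event total, symptomatic and non-symptomatic severe hyponatraemia, severe hyperkalaemia, seizures, other, and then "Number of participants experiencing at least one SAE (% of total number of participants").
- **Laboratory block.** It has its own event total and participant count. It has rows for severe hyponatraemia, split by rate and by magnitude of fall, and for severe hyperkalaemia. A footnote says that it includes events reported before v2.0.

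Section 3.8 expects missing primary-outcome data to be rare because "the plasma sodium measurement is also used to determine one of the key SAEs within the trial, which mandates immediate reporting".

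**The concern.** A child with a severe electrolyte event before v2.0 enters the site-reported total and the any-SAE count. A child with the same event after v2.0 need not. Both are in the denominator, so the printed percentage depends partly on the calendar date of a protocol change and not only on the risk to participants.

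The laboratory block repairs the electrolyte counts, but it stands apart from the first block. No row brings the complete electrolyte data together with seizures and other SAEs, so the any-SAE figure promised in section 3.5 appears only as two partial counts. In a paediatric trial that figure is a main safety result and is likely to be carried from this table into the report.

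Two smaller matters follow from the same change. The symptomatic split exists only in the site-reported block, so it is not systematically available after v2.0. The rationale in section 3.8 also rests on a reporting duty that section 3.5 says has ended.

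**Working it through.** The SAP gives no SAE rate, no date for v2.0 and no number treated before v2.0, so there is no stated figure to reproduce. The check sets the two blocks side by side and then illustrates the effect with assumed values.

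**What each block covers**

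| | Electrolyte SAEs before v2.0 | Electrolyte SAEs after v2.0 | Seizures and other SAEs | Symptom split |
|---|---|---|---|---|
| Site-reported block | yes | not required | yes | yes |
| Laboratory block | yes | yes | no | no |

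Neither line is complete. Both include electrolyte events from before v2.0, so the blocks cannot be added.

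**Footnotes.** In the site-reported block, marker 1 sits on the three electrolyte rows, for example "Acute severe hyponatraemia (symptomatic) n(%)1". Its text is not in the copy available for this review and may carry a caveat. The event total and the any-SAE row carry no marker.

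**Illustration (all inputs assumed, none from the SAP).** Let f be the share treated before v2.0, p the true proportion with an electrolyte SAE, and q the proportion with a seizure or other SAE, independent of p. Suppose that sites report no electrolyte SAEs after v2.0.

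- Site-reported electrolyte percentage over all participants: f × p
- True any-SAE proportion: 1 − (1 − p)(1 − q)
- Site-reported any-SAE proportion: f × [1 − (1 − p)(1 − q)] + (1 − f) × q
- Shortfall in that row: (1 − f) × p × (1 − q)
- Laboratory block: p

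For p = 20% and q = 10%, the true figure is 1 − 0.8 × 0.9 = 28.0%. At f = 0.50 the site-reported row gives 0.50 × 0.28 + 0.50 × 0.10 = 19.0%. The shortfall is 0.50 × 0.20 × 0.90 = 9.0 points.

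| p, q | True any SAE | Site block, f = 0.25 | f = 0.50 | f = 0.75 | Laboratory block |
|---|---|---|---|---|---|
| 10%, 10% | 19.0% | 12.25% | 14.5% | 16.75% | 10.0% |
| 20%, 10% | 28.0% | 14.5% | 19.0% | 23.5% | 20.0% |
| 30%, 20% | 44.0% | 26.0% | 32.0% | 38.0% | 30.0% |

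Adding the blocks does not help. With p = 20%, q = 10% and f = 0.50, 19.0% + 20.0% = 39.0%, against a true 28.0%. The excess of 11.0 points is f × p = 10.0 (events in both blocks before v2.0) plus (1 − f) × p × q = 1.0 (participants after v2.0 with both kinds of SAE).

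The simple factor f × p applies only to the site-reported electrolyte rows. With p = 10% and f = 0.50 those rows show 5.0%. It does not apply to the any-SAE row, which also holds seizures and other SAEs.

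**Symptomatic split.** The laboratory definition has no symptom component. Symptoms are assessed on Days 1 to 3 (section 2.1, visit schedule) and analysed as a secondary outcome (section 3.4), but no planned table links them to a severe sodium fall.

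**The case against.** The strongest reply is that the SAP discloses the change and corrects for it. A reader of the title rows alone might infer that severe hyponatraemia and severe hyperkalaemia are under-reported in this trial. The documents do not support that: the laboratory block is separately labelled and counts both in every participant. Keeping the two sources apart is also defensible, since they are ascertained differently.

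Other stronger readings fail too:

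- **Nothing was reported after v2.0.** The SAP says only that reporting was no longer required. Voluntary reports are possible, and whether symptomatic cases were covered depends on the protocol, which was not available. Any such report shrinks the shortfall illustrated above.
- **Symptomatic hyponatraemia goes unmeasured after v2.0.** Seizures keep their own SAE row, and all four symptoms are analysed by arm in section 3.4. Only the cross-classification is missing.
- **The comparison between arms is biased.** The change applied to both arms, randomisation was stratified by centre and weight and blocked (section 1.5), and SAEs are not tested.
- **The DMC saw short counts.** Section 3.1 says only "The stopping rules will be used as a guideline, alongside the other safety data available to the DMC". It does not say how SAE counts for those reports are compiled, so this would be speculation.
- **Section 3.8 distorts the analysis.** Its outdated sentence supports an expectation about missing data and changes no analysis rule.

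What the reply does not answer is the unmarked total and any-SAE rows, and the absence of any row that combines the sources.

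**Conclusion.** The point holds as a defect in two printed rows and one missing row. As laid out, the site-reported event total and any-SAE percentage combine two ascertainment periods over a single denominator and are likely to undercount, to the extent that sites stopped reporting electrolyte SAEs when no longer required. No row gives participants with any SAE across the whole trial.

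The size of the undercount cannot be computed from the SAP. Under the assumptions above it runs from 2.25 points (19.0% − 16.75%) to 18.0 points (44.0% − 26.0%), and it would be zero if sites had continued to report everything. The effect is on absolute SAE incidence. The incidence of severe hyponatraemia and severe hyperkalaemia as such is covered by the laboratory block, and the primary analysis is untouched.

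**What to change.** 1. In section 4.5, base the event total and the any-SAE row on laboratory-identified electrolyte SAEs in all participants plus site-reported seizure and other SAEs, counting each participant once in the any-SAE row.
2. Show site-reported electrolyte SAEs as a separate line outside that total, restricted to participants treated before v2.0, with their number as the denominator.
3. For the symptomatic and non-symptomatic rows, choose one of two courses. Either label them as covering the period before v2.0 only, or add a descriptive cross-tabulation of laboratory-identified severe hyponatraemia with symptoms recorded on the same day. The second needs a note that same-day occurrence does not show that the sodium fall caused the symptom, since nausea, vomiting and headache may have other causes just after surgery.
4. Reconcile the immediate-reporting sentence in section 3.8 with section 3.5.

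The cost is SAP wording, a revised table shell and modest programming on data already held. No new data are needed. The combined row mixes laboratory-derived and site-reported events, so a footnote should name the source of each component.

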3.6 Sub-Group analyses

A subgroup analysis will be performed for the primary outcome to assess whether the treatment effect differs according to the fluid regimen used in the standard arm. Analysis will be performed using the same methods as for the primary outcome, except the treatment term will be grouped as follows:

- Randomised to Plasmalyte
- Randomised to control and predominantly (defined as >50% total intravenous fluid volume) received 0.9% sodium chloride
- Randomised to control and received 0.9% sodium chloride less than or equal to 50% of their total intravenous fluid volume.

It is anticipated that 0.9% sodium chloride may decrease the number of participants experiencing acute hyponatraemia.

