https://www.who.int/toolkits/growth-reference-data-for-5to19-years will be used to determine the height percentiles. Heights in cm will be converted to inches by dividing by 2.54 and will utilise the height at transplant. The mean minimum and maximum normalised systolic blood pressure, with standard deviation, will be presented separately for each trial arm and overall, for each day. A repeated measures mixed Normal linear regression will be used to assess whether mean percentiles over the three days are different between the two treatment arms, adjusting for donor type (living vs deceased donor), participant weight pre transplant (<20kg vs ≥20kg pre-transplant) and day of measurement. In addition, two random effects will be included in the model to account for individual participant effects and transplant centre. Residual plots from the normal linear regression will be examined. If there is any evidence of skew or non-constant variance, repeated measures mixed normal linear regression of log-transformed percentile will be used to assess whether mean log-percentile are different between the two treatment arms, adjusting for donor type (living vs deceased donor), participant weight pre transplant (<20kg vs ≥20kg pre-transplant) and participant and transplant centre as random effects.

Number of changes in intravenous fluid composition within the first 72 hours post-transplant

A change to intravenous fluid composition will be defined as any modification to the composition of the fluid administered to the participant. The number of changes in fluid will be counted as follows:

- If the participant is initially given something different to which they were randomised, this will be counted as the first change
- Subsequent changes will be counted based on the fluid being administered before the change.
- Diluent used for drug infusions, will not be counted.

For example:

- if the participant was randomised to standard arm, was first administered Hartmann's solution, then 0.9% sodium chloride, and then Hartmann's solution again, this would be counted as two changes.
- If the participant was randomised to Plasma-Lyte, was first administered 5% glucose, then received Plasma-Lyte 148 and then Plasma-Lyte® 148 & Glucose 5%, this would count as three changes.

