- Duration of acute hyponatremia For those participants who experience acute hyponatremia, the total time between transplant operation start time and 72 hours post-transplant when the participant's plasma sodium concentration is below 135mmol/L will be calculated in hours. The start time of an acute hyponatraemia event in this period will be taken as the time of the first test where plasma sodium is <135mmol/L. The corresponding end time will be the time of the first test after this where plasma sodium is ≥135mmol/L, or 72 hours post-transplant, whichever occurs first. For each participant, these event durations will then be totalled. The mean duration, with standard deviation, will be presented for each trial arm and overall. A Normal linear regression model will be used to assess whether mean duration is different between the two treatment arms, adjusting for donor type (living vs deceased donor), participant weight pre transplant (<20kg vs ≥20kg pre-transplant) and transplant centre as a random effect. Residual plots from the normal linear regression will be examined. If there is any evidence of skew or non-constant variance, normal linear regression of log-transformed duration will be used to assess whether mean log-duration are different between the two treatment arms, adjusting for donor type (living vs deceased donor), participant weight pre transplant (<20kg vs ≥20kg pre-transplant) and transplant centre as a random

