| Total intravenous fluid volume received per participant (r | nl/kg body weight) by | time period, Medi | ian (IQR) |
| Intraoperatively | | | , |
| Day 1 | | | |
| Day 2 | | | |
| Day 3 | | | |
| All (intraoperatively to 72 hours post-transplant) | | | |
| Total intravenous fluid volume per participant (ml/kg bod | y weight) by fluid type | e, Median (IQR) | |
| Plasma-Lyte 148 | | | |
| Plasma-Lyte 148 & 5% glucose | | | |
| 0.9% sodium chloride | | | |
| 0.9% sodium chloride with 5% glucose | | | |
| 0.45% sodium chloride | | | |
| 0.45% sodium chloride with 2.5% glucose | | | |
| 0.45% sodium chloride with 5% glucose | | | |
| 10% glucose | | | |
| 4.5% Human albumin solution | | | |
| 5% Human Albumin Solution | | | |
| Hartmann's (Ringer lactate) solution | | | |
| Geloplasma | | | |
| Other | | | |

Statistical Analysis Plan

| | nedication and blood product Randomised | |
|---------------------------------------|--|----------------|
| | Standard care (n=) | Total (n=) |
| Medication - n/N (%) | | |
| Induction Immunosuppression | | |
| Intravenous methylprednisolone | | |
| Basiliximab | | |
| Alemtuzumab | | |
| ATG | | |
| Other | | |
| Corticosteroids | | |
| Prednisolone | | |
| Methylprednisolone | | |
| Calcineurin Inhibitors (CNI) | | |
| Tacrolimus | | |
| Ciclosporin | | |
| Anti-proliferative Immunosuppressants | | |
| MMF | | |
| Azathioprine | | |
| Other Immmunosuppression received | | |
| Immunoadsorption | | |
| Double filtration plasmapheresis | | |
| Rituximab | | |
| Immunoglobulin | | |
| | | |
| Inotropes | | |
| Dopamine Adrenaline | | |
| | | |
| Noradrenaline | | |
| Dobutamine | | |
| Other | | |
| Diuretics | | |
| Furosemide | | |
| Bendroflumethiazide | | |
| Chlorothiazide | | |
| Amiloride | | |
| Spironolactone | | |
| Mannitol | | |
| Insulin | | |
| Antiemetics | | |
| Electrolyte Supplement | | |
| Magnesium | | |
| Potassium | | |
| Sodium bicarbonate | | |
| Sodium Chloride | | |
| | | |
| Blood products received- n/N (%) | | |
| Packed red cell | | |
| Platelets | | |
| Fresh Frozen Plasma | | |
| Other | | |

Statistical Analysis Plan

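### The control-fluid subgroup test does not test whether the effect differs, and both the subgroup split and the duration test compare groups formed after randomisation

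*SAP*

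**What the plan says.** The aim of the subgroup analysis in SAP section 3.6 is "to assess whether the treatment effect differs according to the fluid regimen used in the standard arm". The method is: "Analysis will be performed using the same methods as for the primary outcome, except the treatment term will be grouped as follows". The three levels are all children randomised to Plasma-Lyte, "Randomised to control and predominantly (defined as >50% total intravenous fluid volume) received 0.9% sodium chloride", and "Randomised to control and received 0.9% sodium chloride less than or equal to 50% of their total intravenous fluid volume". No time window is given for the fluid volume, and the Plasma-Lyte arm has no matching split. Section 3.2 and the footnote to the table shell in section 4.6 take the p-value from a likelihood ratio test with and without the treatment term.

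Section 3.4 lists as a secondary outcome "Number of changes in intravenous fluid composition within the first 72 hours post-transplant". The fluid-volume shell in section 4.5 totals fluid from the operation to 72 hours.

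For duration, section 3.5 begins: "For those participants who experience acute hyponatremia, the total time between transplant operation start time and 72 hours post-transplant". It then compares mean duration between arms by Normal linear regression adjusted for donor type, weight and centre. Neither analysis carries a caution, although sections 3.4 and 3.5 do caution readers about the Cox models with competing deaths.

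**The concern.** There are three separate faults.

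1. **Aim and test do not match.** Dropping a three-level term tests equality of all three groups. If Plasma-Lyte works equally well against both kinds of control, the test should still tend to be significant, and a reader may take that as evidence that the effect differs.
2. **The control split is made after randomisation.** The share of 0.9% sodium chloride is an exposure that accrues during care. Nothing confines it to fluid given before the first sodium below 135 mmol/L, so it may be a response to the result it is meant to explain. Each control subset is compared with the whole Plasma-Lyte arm, so neither contrast is randomised.
3. **Duration is tested in a set selected by outcome.** Having an event is the primary outcome, which the trial expects to halve. The children with events in the two arms need not be comparable.

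At stake is a spurious statement about which control fluid the benefit depends on, and a duration comparison that could mislead in either direction.

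**Working it through.** **Design inputs (section 1.6):** 59% control, 29.5% Plasma-Lyte, two-sided 5%, 90% power, 1:1, 128 evaluable, 144 randomised.

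**The plan's own figure.** Two proportions, pooled variance under the null: n per arm = [1.960×√(2×0.4425×0.5575) + 1.282×√(0.59×0.41 + 0.295×0.705)]² / 0.295² = 57.5, so 58 per arm and 116 in total (130 with continuity correction). With O'Brien-Fleming looks at 70, 100 and 128, simulated power at 128 is 91.4%. For drop-out, 128/0.9 = 142.2, so 143, or 144 for equal arms. The stated size is reproduced and is not in dispute.

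**The 2-df test.** Give both control subsets the same event risk, so there is no heterogeneity.
- Log odds ratio = ln[(0.59/0.41)/(0.295/0.705)] = 1.235.
- Variance at 64 per arm = 1/(64×0.59×0.41) + 1/(64×0.295×0.705) = 0.1397.
- Noncentrality = 1.235²/0.1397 = 10.9.
- P(noncentral χ² on 2 df > 5.99) = 0.85. A pooled-variance version gives noncentrality 11.3 and 0.86. An unadjusted likelihood ratio simulation with controls assumed to split 26/38 gives 0.87.
- In that simulation, a 1-df contrast of the two control subsets is significant 5% of the time, as it should be.
- With Plasma-Lyte at 40% instead of 29.5%, the 2-df figure is about 0.47.

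Because the Plasma-Lyte arm is common to both contrasts, it cancels: log OR (Plasma-Lyte v subset A) minus log OR (Plasma-Lyte v subset B) equals log OR (B v A). Heterogeneity as set up here is a comparison of two non-randomised groups of controls.

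**Post-randomisation split.** Assume every child in both arms has risk 59%, with no treatment or saline effect. If a share a of controls with an event and a share b of those without end above 50% saline, the odds ratios against Plasma-Lyte are a/b for the >50% group and (1−a)/(1−b) for the other.

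| a, b (assumed) | OR, >50% saline | OR, ≤50% saline |
|---|---|---|
| 50%, 50% | 1.00 | 1.00 |
| 50%, 40% | 1.25 | 0.83 |
| 60%, 40% | 1.50 | 0.67 |
| 40%, 60% | 0.67 | 1.50 |

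**Duration.** Expected events are 64×0.59 = 37.8 and 64×0.295 = 18.9, so about 57 of 128 children (44%) are analysed, at 2:1 between arms. For illustration, let latent risk L be standard Normal, with an event when L exceeds c = −0.228 (probability 0.59) and duration 12 h × (L − c). The control mean over all children is 12×[φ(c) + 0.228×0.59] = 6.3 h, and among events 6.3/0.59 = 10.6 h.

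| Assumed action of Plasma-Lyte | Events-only mean (control 10.6 h) | All-children mean (control 6.3 h) |
|---|---|---|
| Prevents only the milder episodes (L below 0.539), rest unchanged | 16.8 h | 4.9 h |
| Shifts every child's risk down equally (by 0.766) | 7.6 h | 2.2 h |

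A second model (log-normal duration, median 8 h at average risk, log slope 0.3 on risk, residual log SD 0.6, no fluid effect on the length of any episode that occurs) gives events-only means of 11.9 h control v 13.8 h Plasma-Lyte and all-children means of 7.0 h v 4.1 h. With slope 0 the events-only means are equal, at 9.6 h.

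**The case against.** The best defence is that both analyses are supportive. The modified intention-to-treat primary result stands apart from them, and duration is reported beside the event proportion and the time to first event in all children. If control fluid mostly follows centre practice, the received-fluid split is close to a centre variable and the bias is small; section 1.6 does describe one centre's patients as managed with one fluid. All of this is fair and limits the weight of the point. It does not repair the mismatch between aim and test, and the split is defined on volume received, not on practice.

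Several stronger readings are tempting but unsupported:
- That saline share is measured to 72 hours. Section 3.6 gives no window; 72 hours is an inference from the section 4.5 shell. The missing window is itself a gap.
- That the subgroup p-value is significant whenever Plasma-Lyte works. It is about 85% at the planned effect and about 47% at 59% v 40%.
- That reverse causation is present at a known size. The SAP gives nothing on the strength or direction of any link.
- That the duration test will make Plasma-Lyte look worse. Under a uniform shift in risk, the events-only contrast points the right way.

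The remedies also have limits, which are given with the fix.

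**Conclusion.** The point holds in this form. The test prescribed in section 3.6 does not answer the question that section sets: with no heterogeneity at all, it is significant about 85% of the time at the planned rates. This part rests only on the SAP's own rates and 64 per arm. The subset odds ratios do not identify an unbiased effect; the range of about 0.67 to 1.5 rests on assumed links and collapses to 1.0 without one. The duration test uses about 38 control and 19 Plasma-Lyte children selected by outcome, and the sign and size of its bias depend on how the fluid acts, which is unknown. A reader might infer that these analyses are worthless or that the trial's main conclusion is in doubt. Neither follows: both remain usable as description, and the primary analysis and sample size are untouched. The plan should be changed, but this is not a fault in the primary result.

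**What to change.** **Subgroup (section 3.6 and the section 4.6 shell).** Classify each centre by its usual standard-arm fluid, fixed without reference to participants' outcomes, with a mixed category where needed. Fit arm × centre-fluid group with the primary model's covariates. Report the interaction p-value and the Plasma-Lyte v standard odds ratio within each group. Randomisation is stratified by centre, so those within-group comparisons are randomised. Keep the three-group received-fluid table as description only, state its time window, and attach no heterogeneity p-value. A 1-df contrast of the two control subsets would correct the degrees of freedom but not the post-randomisation split.

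Limits: interaction power will be low with 128 evaluable children; the nine listed centres may not each have one usual fluid; and a difference between centre groups is not itself randomised and could reflect other features of the centres.

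**Duration (section 3.5).** Make the between-arm comparison hours below 135 mmol/L in all modified intention-to-treat participants with sodium data, scoring zero for those without an event, adjusted for weight, donor type and centre, with a bootstrap interval for the mean difference. Report events-only duration descriptively, without a test. Limit: the all-participant measure combines incidence with duration, so it partly restates the primary outcome and should be labelled as such.

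**Cost.** SAP wording, two table shells and one centre-level variable. No new patient data.
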